5 BACKGROUND AND RATIONALE

What is the health care problem?

Bleeding is a common cause of poor health as well as death (1). A recent UK-wide audit showed that acquired bleeding is most commonly seen in patients admitted for trauma, obstetric, surgical, and gastro-intestinal conditions (2). Bleeding affects up to 40% of all trauma patients, up to 30% of all surgery patients and is one of the commonest causes of death for women giving birth (3). However, bleeding is a treatable and preventable cause of death (4). A recognised feature of deaths due to bleeding is that they often occur soon after bleeding begins, or the patient is admitted to hospital. This emphasises the need for timely interventions (5,6).

Research into acquired bleeding has largely been restricted to clinical trials, focussed on single settings or specific groups of patients. For example, the HALT-IT Trial assessed whether treatment with tranexamic acid is safe and reduced mortality in patients with gastrointestinal bleeding (7). These studies tend to include one clearly defined type of patient with major bleeding and address a single research question. This does not permit a broader investigation of variations in treatment and response across different settings and different groups.

Why is research needed?

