6 OBJECTIVES AND OUTCOME MEASURES

Objectives	Outcome Measures	Timepoint(s) of evaluation of this outcome measure (if applicable)
Primary		
To test whether a digital platform can efficiently identify patients who have suffered a bleeding event and	At least 200 patients correctly identified as having suffered bleeding, of which 40 (20%) provide consent	End of study

are willing to consent for the routine blood samples to be used in research.
		

Secondary
		

 1. To conduct a Delphi process with an expert panel to identify criteria that could be applied in the electronic patient record to identify patients with acquired bleeding 2. To use 10 years’ of retrospective data to map bleeding criteria to appropriate data fields within the electronic patient record data sources 3. To encode bleeding criteria into a real-time “algorithm” and display results within a digital web-based platform 4. To measure and refine the accuracy of the algorithm, by manual review of free-text notes of patients identified as bleeding 5. Assess the feasibility of sample sequestering by the lab 6. Assess the feasibility of performing blood clotting and endothelial factor analysis on the sequestered samples. 	
 1. List of bleeding criteria 2. Bleeding criteria mapped to appropriate data fields on the electronic patient record 3. Digital platform capable of identifying bleeding patients in real-time 4. Algorithm accuracy before/after refinement 5. List of unique challenges faced by the laboratory team during blood sample retention and analysis 6. Numbers of samples retained and additional blood clotting and endothelial factor results captured from the retained samples. 	
End of study

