9 PROTOCOL PROCEDURES

9.1 Algorithm development and validation

- Conduct a modified Delphi process using a panel of clinical experts to identify a set of starting criteria (algorithm) e.g. transfusion request or absolute/drop in Hb. In the first instance, we will aim to agree broad criteria that maximise the sensitivity of the algorithm.
- The Clinical Data Warehouse (CDW) is a digital resource within the Oxford University Hospitals NHS Trust (OUH) that will provide up to 10 years of retrospective anonymised patient data to the study. This dataset will comprise demographics and diagnostic/therapeutic codes, hospital locations, admission/discharge timings as well as laboratory results, radiology reports, blood product usage and operative management and outcomes. All data will be time-stamped.
- Using this retrospective patient data, we will develop an algorithm by mapping criteria identified by the Delphi process to routinely-collected data sources. We will combine these mapped criteria into a single algorithm to identify bleeding patients. We will assess its sensitivity to identify patients who have received treatments/investigations for bleeding (e.g. urgent endoscopy, prescription of tranexamic acid, blood transfusions). We will calculate basic demographics (e.g. age, mortality rates) for the patient cohort and compare these to previously published data e.g. from the Trauma Audit Network (TARN) audit. We will also look at how individual criteria overlap to see whether we can identify any redundancy in the list of data sources.
- Sources of patient data required by the algorithm will be integrated into a “real-time” digital platform by processing HL-7 messaging from individual hospital IT systems. This will expand on a pre-existing software platform (developed for the HAVEN Study, <https://ora.ox.ac.uk/objects/uuid:322561c7-866e-4c1e-bcc1-65da4da477fb>) which listens to hospital wide computer systems, integrating relevant data into a real-time research database.
- Using the real-time database, we will implement the algorithm on a lightweight web interface (R Shiny). The interface will include the ability for users to input additional data from the notes review (details below).

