9.4.4 Patients without capacity to consent

Patients who experience an episode of bleeding may transiently experience a lack of capacity to consent, either due to the bleeding itself or the resulting treatment. Bleeding also occurs in those who already lack capacity or in patients who may lose capacity as a result of the event (i.e. trauma with brain injury).

This is a feasibility study trialling a consent model designed to be used in a subsequent interventional trial, of patients during a bleeding episode. A future trial would include randomisation to an intervention, as well as sequestering all available blood samples. Our consent model must be able to include those who lack capacity at the time of bleeding in order to be able to offer an effective future intervention. It is essential that any future study does not exclude those who either had a temporary or permanent lack of capacity, as this would both introduce bias into the study but also deprive the most vulnerable and severely affected from a chance to participate in a study.

Capacity to consent to this study, will be assessed by the clinical team looking after the patient and confirmed by members of the study team. For patients lacking capacity, a personal or professional consultee will be approached.

If a personal consultee is not available, a professional consultee will be consulted. For the purpose of this study, a professional consultee is defined as a clinician (qualified doctor or registered nurse) with

appropriate training (according to local Trust policies) to take on the role of professional consultee. Professional consultees must not be directly involved in the patient's care and cannot be a member of the core study team at site.

If a consultee declines to give consent/advice for the samples and any associated sample data to be retained in the study at any stage, his/her wishes will be respected. A consultee is free to withdraw their support for continuation in the study at any time.

Participants where a consultee has been sought will be visited regularly during their admission, including just prior to discharge. If capacity is regained at any point, then informed consent will be sought. If the patient chooses not to provide consent data and samples will be destroyed. If capacity is not regained, then the samples and data will be included in the planned analysis.

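### The protocol claims real-time identification, but no accuracy or real-time measure takes account of when the flag fires relative to treatment

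*Protocol*

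**What the plan says.** Protocol section 6 lists secondary outcome 3 as "Digital platform capable of identifying bleeding patients in real-time" and secondary outcome 4 as "Algorithm accuracy before/after refinement". Neither mentions when the flag is raised. The Aim in section 5 describes a real-time platform from which patients are approached for research. The lay summary (section 2) adds a test of whether the system could later help find patients for trials. Section 9.4.1 gives speed of identification as one reason for screening without consent. The background notes of deaths from bleeding that "they often occur soon after bleeding begins, or the patient is admitted to hospital".

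For retrospective performance, section 9.1 says: "We will assess its sensitivity to identify patients who have received treatments/investigations for bleeding". Its examples of those treatments and investigations are urgent endoscopy, tranexamic acid prescription and blood transfusion. Its examples of starting criteria for the algorithm are a transfusion request and a low or falling haemoglobin. The same section says of the retrospective data: "All data will be time-stamped".

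In the prospective notes review (also 9.1), nurses record whether they agree with the algorithm and, for wrong flags, the reasons. They are not asked about timing. The variable list in section 11.1.1 names one interval, injury to hospital arrival for patients treated pre-hospital, and does not name the time of the flag.

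**The concern.** A real-time claim is a claim about timing. Sensitivity measured against patients who have already been treated, with no order in time required, answers a different question: whether the record of the admission contains the signal at all. An algorithm that fires early and one that fires once treatment has been requested can earn the same figure.

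The overlap between criteria and reference standard sharpens this. If a transfusion request is a criterion and transfusion is part of the reference, the criterion detects the treatment decision itself. It raises measured sensitivity without showing that the platform found the patient before the clinical team did.

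At stake is what the study can say about secondary outcome 3 and about later use in trials. As planned, a favourable sensitivity would neither support nor refute either.

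**Working it through.** **1. The plan's own figures.** Section 11.2.2 expects about 250 bleeding events in the first three months and assumes 80% sensitivity: 250 × 0.80 = 200 records to review. It aims for 20% of 200 to consent: 200 × 0.20 = 40. Both reproduce. Neither input refers to time.

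**2. What untimed sensitivity can show.** Let N be the admissions with a reference treatment or investigation, A those flagged before it, and B those flagged only at or after it.

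- Any-flag sensitivity: S_any = (A + B) / N
- Late share of true flags: f = B / (A + B)
- Before-treatment sensitivity: S_before = A / N = S_any × (1 − f)

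S_any does not contain f. As f runs from 0 to 1, S_any stays the same while S_before runs from S_any down to 0. Putting in 0.80 only to show these limits: 0.80 × (1 − 0) = 0.80 and 0.80 × (1 − 1) = 0. Nothing in the protocol narrows the range. The 80% in section 11.2.2 is a prospective planning assumption about bleeding events, not the retrospective sensitivity of section 9.1, so even the upper limit is illustrative.

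**3. The measures side by side.**

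- Retrospective sensitivity (9.1): judged against treatment already received; no order in time stated.
- Notes review (9.1): agreement, and reasons for wrong flags; no timing.
- Secondary outcome 3 (6): a capability; no measure of delay.
- Secondary outcome 4 (6): accuracy before and after refinement; no timing.
- Primary outcome (6): "At least 200 patients correctly identified as having suffered bleeding, of which 40 (20%) provide consent"; no timing, and none needed for what it asks.

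**4. The overlap.** A transfusion request normally precedes the transfusion. A flag built on the request would therefore pass a rule that it must come before transfusion, although the decision to treat has been made. Timing alone does not remove this; sensitivity must also be reported without such criteria.

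**The case against.** The strongest reply is that this study does not test enrolment during bleeding. Its primary objective begins: "To test whether a digital platform can efficiently identify patients who have suffered a bleeding event and". The rest concerns consent for use of routine samples, which may be sought up to 28 days after the episode (section 9.4.3). A flag raised after treatment does not defeat that. This stands, and it confines the point to secondary outcome 3, the accuracy measures and the lay summary's question about future trials.

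Several stronger readings are tempting and are not supported:

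- A reader might infer a rule that a flag at any time counts as success. No such rule is stated. The wording in section 9.2 about any point in the admission concerns destruction of data. The gap is the absence of a timing rule.
- Section 9.4.4 contains the phrase "designed to be used in a subsequent interventional trial, of patients during a bleeding episode". What is so designed there is the consent model, so it sets no speed requirement for the algorithm.
- Diagnostic and therapeutic codes might seem to bring late information into the flag. They are listed as contents of the retrospective dataset, not as criteria. The algorithm must also run on live feeds, where data absent during the admission could not trigger it.
- A reader might expect late-firing criteria to be kept. No rule retains criteria by sensitivity alone; the panel later refines the algorithm for specificity.

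The SAP is not shown and may set how flags and treatments are matched in time. That is a fair reservation about the analysis of sensitivity. It does not supply a timing element to the outcome measures, which the protocol itself fixes in section 6.

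Finally, a flag before the first treatment is not the same as a flag during bleeding, since bleeding may continue after treatment starts. This also stands: the timed measure is a proxy and should be reported descriptively.

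**Conclusion.** The point holds as a limited one. The protocol claims real-time identification and wants to learn about suitability for later trials, but its sensitivity, accuracy and real-time outcomes are the same whether flags come before or after treatment. The example overlap between transfusion request and blood transfusion shows how this could arise under the protocol's own wording. The primary outcome is unaffected.

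No magnitude can be given. Assumed late shares of 25% or 50% would turn 80% into 60% or 40% (0.80 × 0.75 and 0.80 × 0.50), but those results only restate the assumption. The conclusion rests on the protocol as written and on the example criteria; the panel's final list may differ. It is an inexpensive improvement worth making, not a flaw that undermines the study.

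**What to change.** In section 9.1, using the time-stamped data:

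- report retrospective sensitivity for any flag in the admission and, beside it, for a flag time-stamped before the first reference treatment or investigation;
- build each flag only from values already available at that moment;
- report sensitivity again with criteria that duplicate the reference standard removed.

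For secondary outcome 3 in section 6, report descriptively, as median and interquartile range, the time between the flag and the first recorded treatment or investigation in the prospective periods, from platform time stamps. This assumes that the platform logs when each flag is raised; the protocol should say so. A nurse-entered time of first documented bleeding is an optional addition. It would have to be in the interface before the reviews begin, and it means abstracting times from free text.

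The cost is wording and a little more analysis. Timed sensitivity cannot exceed the untimed figure and will probably be lower. No change to design, consent or clinical care is involved.

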- Research nurses will use the interface to identify (up to 200) patients who are potentially bleeding and review their free-text notes in the electronic patient record, notifying attending clinicians when there is no documentation of bleeding. Using the additional clinical information in patients’ notes, the nurses will record whether they agree with the output of the algorithm. Where the algorithm has incorrectly identified patients as having bled, the nurses will record the reasons for bleeding based on the clinical information in the notes.
- The expert panel will review the results of the notes review and refine the algorithm to increase its specificity.
- The expert panel will not have any access to confidential patient information.

9.2 Consent patients identified by system for use of surplus routine blood samples in research analysis.

In the final three months of the study, we will prospectively test the accuracy of the algorithm and the feasibility of using the real-time platform for consenting patients to use their data and routine blood samples for future research.

When the algorithm identifies that a patient has met the criteria for bleeding, the platform will:

- Allocate the patient a RE-BLEED study ID.

- Electronic Hospital Record (EHR) data for this entire encounter will be retained in the study database and when the encounter ends the record will be pseudo-anonymised.
- A notification will be sent to the main hospital laboratory requesting that their (left-over) blood samples, once all clinical testing has been completed as part of routine clinical care, be retained for use in the study, pending patient consent. Where consent is not given, the samples will be destroyed as per local protocols.

In order to be able to screen all patients in the hospital, the system must collect data for all adult patients from their admission to their discharge. The records of adult patients admitted to the hospital who do not meet the eligibility at any point during their admission will be destroyed at the point they are discharged from hospital.

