11.1.2 Descriptive statistics

We will calculate summary statistics (e.g. demographics, treatments, mortality,) for both the retrospective and prospective cohorts identified by the algorithm.

For continuous variables we will use the median/interquartile range; for binary or categorical variables we will use the proportion. Confidence intervals for proportions were calculated using the Pearson-Klopper method. We will be able to make compare event rates with previously published data (UK, USA, Europe).

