11.1.3 Retrospective cohort

As part of algorithm development we will perform additional analyses on the retrospective cohort. These will include exploring specific subgroups (obstetric, gastro-intestinal, emergency surgery, trauma) and examining treatment rates (e.g. rates of tranexamic acid use in post-partum haemorrhage). Results of these more detailed analyses will be compared with previously published data and current clinical guidelines.

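### Benchmark comparisons use the whole flagged cohort, so a difference from published figures cannot be split into case mix and false positives

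*Protocol*

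**What the plan says.** Section 9.1 describes building the algorithm on retrospective data. After a sensitivity check against treatments and investigations for bleeding, it calculates basic features such as age and mortality for the patient cohort and will "compare these to previously published data e.g. from the Trauma Audit Network (TARN) audit". The sentence does not restrict the cohort to trauma.

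Section 5 says that "acquired bleeding is most commonly seen in patients admitted for trauma, obstetric, surgical, and gastro-intestinal conditions", and section 9.5 says the platform looks for acquired bleeding of any severity. The starting criteria are deliberately wide: "we will aim to agree broad criteria that maximise the sensitivity of the algorithm". Specificity is raised only afterwards: "The expert panel will review the results of the notes review and refine the algorithm to increase its specificity".

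Section 11.1.2 produces summary statistics, including treatments and mortality, "for both the retrospective and prospective cohorts identified by the algorithm". It then foresees comparing event rates with published UK, US and European data.

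Section 11.1.3 adds analyses of the retrospective cohort: "These will include exploring specific subgroups (obstetric, gastro-intestinal, emergency surgery, trauma) and examining treatment rates". Those results are also to be compared with published data and with guidelines.

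**The concern.** Published figures on bleeding describe patients who bled, usually from one type of cause. The cohort in 9.1 and 11.1.2 differs from that in two ways. It pools types of bleeding whose age and mortality can be expected to differ, and it contains patients who did not bleed. Both shift the observed rates, and the plan as worded offers no means of telling one shift from the other.

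The nurses' verdicts on flagged patients, recorded under 9.1, would identify false positives among the reviewed prospective patients, but 11.1.2 does not use them. At stake is how the descriptive tables are read. A mortality or treatment rate that differs from a published figure could be put down to local practice, to the algorithm or to case mix, and the table would not help the reader choose. Rates close to a published figure are equally ambiguous.

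**Working it through.** The protocol states no figure on this point, so there is none to reproduce. It gives no positive predictive value (PPV), case-mix share or mortality rate. Every rate below is an assumption chosen to show the mechanism.

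**1. What is compared with what**

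| Section | Set summarised | Benchmark | Limited to confirmed bleeders? |
|---|---|---|---|
| 9.1 | The patient cohort (retrospective) | Published data, trauma audit as example | No |
| 11.1.2 | Both cohorts as flagged | UK, US, European data | No |
| 11.1.3 | Four subgroups, retrospective only | Published data, guidelines | No |

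Reading the 9.1 cohort as everyone flagged is an inference. The wording of 11.1.2 supports it.

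**2. Whole flagged cohort, mortality**

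Formula: PPV × [w × m_trauma + (1 − w) × m_other] + (1 − PPV) × m_false.

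Assumptions: m_trauma 15%; trauma share of true bleeds w 10-40%; m_other 3-15%; m_false 2-5%.

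The lowest value uses w = 10%, m_other = 3% and m_false = 2%. The bracket is then 0.1 × 0.15 + 0.9 × 0.03 = 0.042. The highest uses m_other = 15% and m_false = 5%, where the bracket is 0.15 for any w.

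| PPV | Lowest | Highest |
|---|---|---|
| 0.3 | 0.3 × 0.042 + 0.7 × 0.02 = 2.7% | 0.3 × 0.15 + 0.7 × 0.05 = 8.0% |
| 0.6 | 0.6 × 0.042 + 0.4 × 0.02 = 3.3% | 0.6 × 0.15 + 0.4 × 0.05 = 11.0% |
| 0.9 | 0.9 × 0.042 + 0.1 × 0.02 = 4.0% | 0.9 × 0.15 + 0.1 × 0.05 = 14.0% |

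The ranges overlap from 4.0% to 8.0%. For example, 8.0% arises at PPV 0.3 (last column). It also arises at PPV 0.9 with w = 10%, m_other = 8% and m_false = 2%: 0.9 × (0.015 + 0.072) + 0.1 × 0.02 = 8.0%. The same result fits a poor and a good algorithm.

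**3. Trauma subgroup only**

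Formula: PPV × m_trauma + (1 − PPV) × m_false, assuming the same PPV and m_false within the subgroup.

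| PPV | m_false 2% | m_false 5% |
|---|---|---|
| 0.3 | 5.9% | 8.0% |
| 0.6 | 9.8% | 11.0% |
| 0.9 | 13.7% | 14.0% |

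These ranges do not overlap, so matching by type makes the comparison more informative. The separation depends on holding trauma mortality at 15%. If it were 10%, PPV 0.9 with m_false 2% would give 0.9 × 0.10 + 0.1 × 0.02 = 9.2%, below the band for PPV 0.6. Matching removes differences between bleeding types but not differences within a type.

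**4. False positives alone**

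Assume mortality of 10% in bleeders and 2% in false positives, and a treatment given to 80% of bleeders and to no false positives.

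| PPV | Mortality shown (10% in bleeders) | Treatment rate shown (80% in bleeders) |
|---|---|---|
| 0.8 | 0.8 × 10 + 0.2 × 2 = 8.4% | 64% |
| 0.5 | 0.5 × 10 + 0.5 × 2 = 6.0% | 40% |
| 0.3 | 0.3 × 10 + 0.7 × 2 = 4.4% | 24% |

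False positives can therefore move a published-data comparison materially even when case mix is matched.

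**The case against.** The strongest reply is that little rests on this comparison and that much of the remedy is already planned.

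- **The trauma audit is only an example.** Section 9.1 introduces it as one source, and 11.1.2 names wider sources. A reader might infer that a trauma audit is the benchmark for every type of bleeding; the text does not say so. This stands.
- **Subgroups are planned.** Section 11.1.3 belongs to algorithm development, includes trauma, and compares subgroup results with published data. This stands for the retrospective cohort. It does not say that the 9.1 comparison uses those subgroups, it does not remove false positives, and it does not cover the prospective cohort.
- **Accuracy is assessed elsewhere.** Sensitivity, the notes review and the prospective test in the final three months serve that purpose. Section 11.4 states that there are no decision points. A reader might infer from the heading of 9.1 that agreement with published mortality is meant to validate the algorithm, but no agreement criterion is set and no conclusion is tied to it. This stands.
- **Describing everyone flagged is legitimate in a feasibility study of the platform.** That is true of a description. It does not justify setting the same rates beside figures for confirmed bleeders without qualification.
- **Analysis sets may be left to the statistical analysis plan.** Section 11.3 does leave exclusions to that plan, which is not at hand. The criticism is limited to what 11.1.2 already fixes, namely the flagged cohorts as the set to be summarised.

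**Conclusion.** The concern holds as a modest, inexpensive improvement. As worded, 9.1 and 11.1.2 compare rates from a mixed cohort containing false positives with published data on bleeding patients, and a difference cannot be attributed to either source. In the illustration, whole-cohort mortality overlaps heavily across PPVs of 0.3 to 0.9. The direction of the argument needs only that some flagged patients did not bleed and that rates differ by type of bleeding and between bleeders and non-bleeders. The sizes rest wholly on assumed rates.

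Three stronger readings are not supported:

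- That the comparison says nothing at all. A gross mismatch is still a descriptive signal of implausibility.
- That only in-hospital mortality can be available. Section 9.1 lists outcomes among the retrospective data, and the encounter-based retention in 9.2 concerns the prospective platform. The protocol simply does not define the time window.
- That mortality is missing from the data because the 11.1.1 list omits it. Outcomes are in the retrospective dataset and 11.1.2 names mortality as a summary.

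**What to change.** **Section 9.1:** state that comparison with the trauma audit uses the trauma subgroup of 11.1.3, and that each other subgroup is compared with published data for the same type of bleeding.

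**Section 11.1.2:** base the prospective comparison with published event rates on flagged patients whom the nurses confirmed as having bled, and show all flagged patients alongside.

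**Retrospective cohort:** label the comparison as descriptive and as including unconfirmed cases. Correcting it with a PPV carried back from the prospective notes review is not advisable. That would also need event rates among retrospective false positives, which the plan does not measure.

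**Cost:** a few sentences and some extra tables, using verdicts already being collected. The downside is smaller denominators. Of the 200 records planned for review in section 11.2.2, 180, 120 or 60 would be confirmed at a PPV of 0.9, 0.6 or 0.3 (200 × PPV), and any split by type of bleeding would be smaller still. The confirmed set exists only for patients whose notes are reviewed, and the tables should say so.

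### For wrongly flagged patients the notes review asks why they bled, not why the flag was wrong; the verdict is also recorded as agreement with a known flag

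*Protocol*

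**What the plan says.** Section 9.1 of the protocol sets out the notes review used to refine the algorithm:

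- Selection: "Research nurses will use the interface to identify (up to 200) patients who are potentially bleeding and review their free-text notes". Only flagged patients are reviewed.
- Verdict: "Using the additional clinical information in patients’ notes", "the nurses will record whether they agree with the output of the algorithm".
- False positives: "Where the algorithm has incorrectly identified patients as having bled, the nurses will record the reasons for bleeding", drawing on the clinical information in the notes.
- Use: "The expert panel will review the results of the notes review and refine the algorithm to increase its specificity".
- Limit on the panel: "The expert panel will not have any access to confidential patient information".

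Secondary objective 3 (section 6) is to encode the criteria and "display results within a digital web-based platform". Section 9.1 adds that users can enter data from the notes review in that interface. Secondary objective 4 measures and refines accuracy through manual review of the flagged patients.

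**The concern.** The main issue is the item collected for false positives. The starting criteria in section 9.1 are deliberately broad so that sensitivity is high, and false flags are therefore expected. Raising specificity depends on knowing what caused them. The sentence that should collect this information asks instead for the causes of an event that, by its own premise, did not occur. A form built literally from it would hold a blank or a meaningless entry for the patients the panel most needs to understand.

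The second, smaller issue is the verdict. The nurse reaches each record through the flag and then states agreement or disagreement with it. A reader who knows the result under test may lean towards it, most easily in borderline cases. Section 9.5 counts bleeding of any severity, so borderline cases are likely. The accuracy result under objective 4 rests on this verdict.

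**Working it through.** **1. The plan's own figure.** Section 11.2.2 expects about 250 bleeding events in the first three months and assumes 80% sensitivity: 250 × 0.80 = 200 records to review. This reproduces exactly. The product counts bleeding patients who are detected. It says nothing about how many flags are false, and the protocol states no PPV anywhere.

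**2. The contradiction, side by side.**

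| Step in section 9.1 | What it requires |
|---|---|
| Condition | The algorithm flagged the patient, and the nurse judges that the patient did not bleed |
| Item to record | Reasons for bleeding |
| Next use | The panel raises specificity, that is, removes false flags |

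The condition and the item cannot both hold for the same patient. The next use needs the cause of the false flag, which the item does not ask for.

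**3. How many records this touches.** The number with the wrong item is 200 × (1 − PPV). PPV is an assumption here:

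- PPV 50%: 200 × 0.50 = 100
- PPV 70%: 200 × 0.30 = 60
- PPV 90%: 200 × 0.10 = 20

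**4. What agreement framing could do to the accuracy estimate.** Let b be the share of false positives that the nurse wrongly accepts, and m the share of true bleeds wrongly rejected, for example because they were not documented. Then

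apparent PPV = PPV + b(1 − PPV) − m·PPV.

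The protocol gives none of these three values. For illustration only, with PPV 70%:

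- b = 10%, m = 0: 0.70 + 0.10 × 0.30 = 0.73
- b = 25%, m = 0: 0.70 + 0.25 × 0.30 = 0.775
- b = 10%: the two errors cancel when m = 0.10 × 0.30 / 0.70 = 0.043, and a larger m makes the apparent PPV too low.

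Neither the size nor the sign of the bias can be derived from the document.

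**The case against.** **A drafting slip.** The faulty sentence follows the agreement item and precedes the step on specificity, so the intended meaning is fairly clear: record why the patient was wrongly flagged. Staff may well do that. This stands as a reading of intent. It does not rescue the wording, which is the operative instruction.

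**Other information for the panel.** A reader might infer that false positives will go unexplained, or that the nurses' entries are the panel's only evidence. The documents do not support that. The panel is barred from confidential patient information, not from all study data. The agreement item itself marks which flags were false. Section 9.1 also plans to examine how criteria overlap in the retrospective data. The protocol does not say that the panel will see which criteria fired for each reviewed patient, but it does not exclude it.

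**The agreement item.** Among flagged patients only, agreeing is logically the same as judging that the patient bled. Renaming the field adds no independence by itself. The verdict also rests on a separate source, the free-text notes, and nurses must check for documented bleeding because they notify clinicians when there is none. These arguments stand, and they reduce this part to an improvement. What remains is that the verdict is unblinded and that section 9.1 describes no bleeding definition for the review, although a working instruction not shown here might hold one.

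**Conclusion.** The self-contradiction in section 9.1 is established from the text alone and needs no assumption. Followed literally, the instruction collects the wrong item for every false positive. The number of such records is unknown; the range of 20 to 100 out of 200 rests on an assumed PPV of 90% down to 50%.

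The agreement framing is a secondary weakness. It may bias the accuracy estimate by an amount that cannot be computed. Two stronger inferences should not be drawn:

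- That PPV will be inflated. Anchoring would push it up, but true bleeds missing from the notes could push it down.
- That the primary count of at least 200 correctly identified patients is biased by this form. The procedure belongs to the refinement stage, and the consent target belongs to the second three-month period. Section 9.2 says that accuracy will be tested then, but not that the same agreement item is used. Carry-over is plausible but not stated.

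**What to change.** **Correct the sentence (wrong as written).** For patients incorrectly identified, have the nurses record *the reasons the patient was incorrectly identified (criterion that triggered the flag and the non-bleeding explanation found in the notes)*. This is a one-line change with a matching field on the form, and needs no extra records or staff. If the review has already taken place, check what the form in use actually asked.

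**Improve the verdict (optional, cheap).** Replace the agreement item with bled, did not bleed or unclear, judged against a written bleeding definition. If the interface shows which criteria fired, which the protocol does not state, have the verdict saved before they are displayed. The cost is form and interface wording plus agreeing the definition. The downside is that the nurse still knows the record was flagged, so anchoring is reduced and not removed.
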